### 3.2 Schedule of Events

**Table 1 Schedule of Events**

Study Visits	Screening (up to D-28)	Randomization a (phone)	Treatment Period					Follow-up/ET (Day 56/Week 8)
			D1	D8 (Week 1)	D15 (Week 2)	D22 (Week 3)	D28 (Week 4)	
Window (days)			0 days	±1 day	±2 days	±2 days	±2 days	-2 days
Informed consent	X							
Demographics	X							
Medical and surgical history	X		X					
Inclusion-exclusion criteria	X		X					
Pregnancy test (WOCBP only)	Serum		urine	urine	urine	urine	urine	urine
Clinical laboratory tests (biochemistry, hematology, urinalysis)	X		X		X		X	X
Body weight and height, BMI b	X		X		X		X	X
Serology (HIV, HBV, HCV)	X							
Physical examination	X		X		brief		X	brief
Vital signs	X		X	X	X	X	X	X
Electrocardiogram (12-lead, central reading)	X c		X d		X e		X d	X f
vIGA	X		X		X		X	X
BSA (excluding palms, scalp, axillae, groin, genitals, and folds)	X		X		X		X	X
EASI	X		X		X		X	X
5-D pruritus scale			X		X		X	X
DLQI			X		X		X	X
POEM			X		X		X	X
Pruritus NRS g	X		X	X	X	X	X	
Randomization		X						

Study Visits	Screening (up to D-28)	Randomization a (phone)	Treatment Period					Follow-up/ET (Day 56/Week 8)
			D1	D8 (Week 1)	D15 (Week 2)	D22 (Week 3)	D28 (Week 4)	
Window (days)			0 days	±1 day	±2 days	±2 days	±2 days	-2 days
Investigational Product Application at study site			X	X	X	X		
Investigational Product BID Application Daily b			X -----		X		X g	
Participant Daily e-Diary i			X -----		X		X	
Investigational product distribution			X	X	X	X		
Collection of investigational product				X	X	X	X	X f
Verification of daily diary			X	X	X	X	X	X
Emollient use	-7 days	X a	X -----		X			
Local tolerability assessments			X	X	X	X	X	X
PK samples collection			See Table 2					
Concomitant medication	X	X	X	X	X	X	X	X
Adverse events evaluation	X	X	X -----					X

BID=twice daily; BMI=body mass index; BSA=body surface area; D=day; DLQI=Dermatology Life Quality Index; EASI=Eczema Area and Severity Index; ECG=electrocardiogram; ET=early termination; HBV=hepatitis B virus; HCV=hepatitis C virus; HIV=human immunodeficiency virus; NRS=numerical rating scale; PK=pharmacokinetics; POEM=Patient-Oriented Eczema Measure; vIGA= Validated Investigator Global Assessment; WOCBP=women of childbearing potential.

Note: In general, non-invasive procedures should be completed prior to invasive procedures. Unless otherwise specified, the study assessments scheduled during the study visits will be performed before the study product application. If assessments are scheduled for the same nominal time, then the assessments should occur in the following order, when possible: vital signs, 12-lead ECG, local tolerability, pruritus NRS, and blood draw for PK evaluation.

a The Randomization visit will be conducted remotely via phone after all screening assessments have been completed and the results of those assessments are determined to be in line with the trial entry criteria (i.e., based on central read ECG, central laboratory results, and all clinical outcome assessments and patient-reported outcome assessments). During this remote check-in, study staff will verify the participant's desire to continue in the trial, record any adverse events, assess concomitant medications, and confirm that nonprescription emollient has been (or will be) used consistently for at least 7 days prior to Day 1. Study staff will then acquire a randomization number for eligible participants, which will prompt shipment of investigational product to the study site. The interval between the Randomization Visit and Day 1 Visit should allow enough time for the investigational product to arrive at the study site (i.e., approximately 1 week).

b Height will be measured only at screening and the same value will be used for BMI calculation at other visits.

c If participant has clinically significant 12-lead ECG abnormalities (per Investigator) or QTcF >450 ms, abnormal ECG may be repeated once. For participants with QTcF >450 ms on initial ECG, the mean of the 2 QTcF assessments will determine eligibility.

d On Day 1 and Day 28, ECGs will be time matched with PK sample collection and will be performed at time 0 (pre-dose, within 1 hour of dosing), 1 (±15 min), 2 (±30 min), and 4 (±1 hour) hours post-dose. The ECG should be performed prior to the PK sample collection.

e ET only.

f Hourly starting immediately post dose until bedtime on Day 1 only.

g Should not be applied to palms, scalp, axillae, groin, genitals, or folds. The last dose of investigational product should be applied during the Day 28 study visit; participants are not to receive study treatment for more than 28 days.  
h Participant will complete daily e-diary onsite during visit if not already completed.

[figure not shown]
**Table 2 Pharmacokinetic Sampling**

Window	Predose	Post IP Administration		
		1 hour	2 hours	4 hours
		± 15 min	± 30 min	± 1 hour
Day 1	X	X	X	X
Day 28 (-2 days)	X	X	X	X

IP=investigational product

### 3.3 Study Design Schema

**Figure 1 Trial Design**

## **4 ANALYSIS SETS**

### **4.1 Modified Intent-to-Treat Analysis Set**

Modified intent-to-treat analysis (mITT) analysis set includes all randomized participants who meet inclusion and exclusion criteria at the Day 1 visit and receive at least 1 dose of treatment. Participants will be attributed to the treatment they are randomized regardless of the actual treatment they receive.

### **4.2 Per-Protocol Set**

The Per-Protocol (PP) set includes all participants who were randomized, received at least 1 dose of study product without any major protocol deviations that may affect the efficacy outcome, received the treatment they were randomized to, who don't have missing baseline pruritus NRS, who don't have 50% or more missing pruritus NRS data in week 4. Those who discontinue the study treatment prior to NRS week 4 will also be excluded. The participants to be excluded from the per protocol set due to the major protocol deviations will be evaluated and determined prior to database lock by the sponsor.

### **4.3 Safety Set**

The safety set includes all participants who receive at least 1 dose of treatment. Participants will be attributed to the initial actual treatment they receive.

### **4.4 Pharmacokinetic Set**

The Pharmacokinetic (PK) set will include all participants who received at least 1 dose of treatment and have ASN008 concentration data.

## 5 GENERAL CONSIDERATIONS

### 5.1 Sample Size

For the primary endpoint analysis of the percent change of 7-day average daily peak pruritus NRS from Baseline to Week 4, N = 24 / group will give us 80% power to detect a standardized effect of 0.72 with 2-sided significance level of 0.1 (28.8% improvement over placebo in % change from baseline in pruritus, assuming standard deviation [SD] = 40%).

### 5.2 Baseline

Unless otherwise specified, baseline value will be defined as the last non-missing assessment prior to or on the first study treatment application date and time (including unscheduled assessments). If the last non-missing assessment is performed on the same date as the first study treatment and time is not available, the assessment will be considered as baseline, except for adverse events (AEs) and medications starting on the first study treatment dose date, which will be considered post-baseline.

### 5.3 Study Day

Study day will be calculated from the first study treatment date and will be used to show start/end day of assessments or events.

- For dates on or after the first treatment date, Study Day = Date – First Study Treatment Date + 1.
- For dates before the first treatment date, Study Day = Date – First Study Treatment Date.
- Study day will be set to missing when the assessment/event date is partial or missing.

### 5.4 Descriptive Statistics

All continuous variables will be summarized by the number of participants, mean, SD, median, minimum, and maximum. Categorical variables will be presented as frequencies and percentages. Summary tables will be presented by treatment and visit, when applicable.

- Change from baseline will be calculated as:
  - Assessment value at post-baseline visit X – baseline value.
- Percent change from baseline will be calculated as:
  - $(\text{Assessment value at post-baseline visit X} - \text{baseline value}) / \text{baseline value} \times 100$ .

### 5.5 Treatment Grouping

The participants will be grouped by ASN008 gel at 1.25, 2.5, or 5%, or Vehicle BID.

### 5.6 Handling of Retests, Unscheduled Visits, and Early Termination Data

When retests measurements are done, the retest measurement will be used for the summary analysis. All data from all visits will be listed.

Unscheduled visit assessment will be listed and will not be included in by-visit outputs.

All safety data will be included in the non-by-visit summary tables/figures. Besides, data from unscheduled visits will be listed.

Early Termination visit assessments will be summarized as a separate visit in by-visit outputs.

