Note: In general, non-invasive procedures should be completed prior to invasive procedures. Unless otherwise specified, the study assessments scheduled during the study visits will be performed before the study product application. If assessments are scheduled for the same nominal time, then the assessments should occur in the following order, when possible: vital signs, 12-lead ECG, local tolerability, pruritus NRS, and blood draw for PK evaluation.

^a The Randomization visit will be conducted remotely via phone after all screening assessments have been completed and the results of those assessments are determined to be in line with the trial entry criteria (i.e., based on central read ECG, central laboratory results, and all clinical outcome assessments and patient-reported outcome assessments). During

this remote check-in, study staff will verify the participant's desire to continue in the trial, record any adverse events, assess concomitant medications, and confirm that non-prescription emollient has been (or will be) used consistently for at least 7 days prior to Day 1. Study staff will then acquire a randomization number for eligible participants, which will prompt shipment of investigational product to the study site. The interval between the Randomization Visit and Day 1 Visit should allow enough time for the investigational product to arrive at the study site (i.e., approximately 1 week).

^b Height will be measured only at screening and the same value will be used for BMI calculation at other visits.

^c If participant has clinically significant 12-lead ECG abnormalities (per Investigator) or QTcF >450 ms, abnormal ECG may be repeated once. For participants with QTcF >450 ms on initial ECG, the mean of the 2 QTcF assessments will determine eligibility.

^d On Day 1 and Day 28, ECGs will be time matched with PK sample collection and will be performed at time 0 (pre-dose, within 1 hour of dosing), 1 (± 15 min), 2 (± 30 min), and 4 (± 1 hour) hours post-dose. The ECG should be performed prior to the PK sample collection.

^e ET only.

^f Hourly starting immediately post dose until bedtime on Day 1 only.

^g Should not be applied to palms, scalp, axillae, groin, genitals, or folds. The last dose of investigational product should be applied during the Day 28 study visit; participants are not to receive study treatment for more than 28 days.

^h Participant will complete daily e-diary onsite during visit if not already completed.

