13. Current excessive sun exposure, planning a trip to a sunny climate during trial participation, or use of tanning beds/booths within 4 weeks prior to Day 1; or is not willing to minimize natural and artificial sunlight exposure during the trial. Use of sunscreen products on non-treatment areas (except those containing Vitamin C) and protective apparel are recommended when exposure cannot be avoided.
14. Known hypersensitivity to ASN008 or its excipients.
15. Known history of clinically significant drug or alcohol abuse in the last year prior to Day 1.
16. Close affiliation with the Investigator (e.g., a close relative) including site staff, persons working at the contract research organization, or Sponsor employee.
17. Any clinically significant medical condition or physical/laboratory/ECG/vital signs abnormality that would, in the opinion of the Investigator, put the participant at undue risk or interfere with interpretation of trial results.
 - a. Participant has 12-lead ECG abnormalities, at screening or Day 1, considered by the Investigator to be clinically significant or QTcF >450 ms, regardless of clinical significance. Abnormal ECG may be repeated once. For participants with QTcF >450 ms on initial ECG, the mean of the 2 QTcF assessments will determine eligibility.
18. History of congestive heart failure, defined as New York Heart Association class III or class IV.
19. History of significant arrhythmias (e.g., supraventricular tachycardia, atrial fibrillation, atrial flutter, ventricular tachycardia).
20. History of erythrodermic, refractory or unstable skin disease, including AD, that requires frequent hospitalizations and/or frequent intravenous treatment for skin infections over the last year.
21. History of eczema herpeticum within 12 months, and/or a history of 2 or more episodes of eczema herpeticum at any time prior to enrollment.
22. Major surgery within 8 weeks prior to Day 1 or major surgery planned during the trial.
23. Known immune deficiency or immunocompromise.

24. Positive results for hepatitis B surface antigens, antibodies to hepatitis B core antigens, hepatitis C virus, or human immunodeficiency virus at the screening visit.
25. Presence of any of the following laboratory abnormalities at the screening visit:
 - a. Hemoglobin <10 g/dL.
 - b. Platelet count $\leq 125 \times 10^3$ / μ L.
 - c. Neutrophils $\leq 1.5 \times 10^3$ / μ L.
 - d. Lymphocytes $\leq 1.0 \times 10^3$ / μ L.

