8.1. Safety Parameters

8.1.1. Vital Signs

The following vital signs will be recorded at the visits specified in [Table 2](#) with the participant in a seated position, after having sat calmly for at least 5 minutes:

- Systolic and diastolic BP (mmHg)
- Pulse (beats per minute)
- Respiration rate (breaths per minute)
- Body temperature (°C)

The Investigator will review all vital sign results. Measurements of systolic BP >160 mmHg or diastolic BP >95 mmHg at Screening or Day 1 must be confirmed by 1 repeat assessment in order to determine eligibility. Values that are outside of the normal reference ranges at subsequent time points during the trial may be repeated at the discretion of the Investigator.

If deemed appropriate by the Investigator, clinically significant findings in the vital signs will exclude a participant from study participation. Any abnormal finding related to vital signs that the Investigator considers to be clinically significant must be recorded as an AE.

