Urinalysis	Color, clarity, pH, specific gravity, bilirubin, glucose, ketones, leukocytes, nitrite, blood, protein, urobilinogen and microscopic analysis (as required)
Pregnancy test	For females of childbearing potential (serum pregnancy test (β -hCG) at screening and serum or urine pregnancy test at other visits)
Laboratory tests required at screening only	FSH levels for females who had a cessation of menses for at least 12 months without an alternative medical cause Serology (HBV [HBsAg, anti-HBc], HCV, HIV)

ALT=alanine aminotransferase; anti-HBc=antibody to hepatitis B core antigen; AST=aspartate aminotransferase; β -hCG= β -human chorionic gonadotropin; BUN=blood urea nitrogen; FSH=follicle-stimulating hormone; GGT=gamma-glutamyl-transferase; HBsAg=hepatitis B surface antigen; HBV=hepatitis B virus; HCT=hematocrit; HCV=hepatitis C virus; Hgb=hemoglobin; HIV=human immunodeficiency virus; LDH=lactate dehydrogenase; MCH=mean corpuscular hemoglobin; MCHC=mean corpuscular hemoglobin concentration; MCV=mean corpuscular volume; PLT=platelets; RBC=red blood cell (count); WBC=white blood cell (count).

Participants who do not qualify to participate in the trial due to a screening laboratory value abnormality may repeat the test once within the original screening time window, if the Investigator believes there is a reasonable possibility that the participant may be eligible if re-tested.

If deemed appropriate by the Investigator, clinically significant findings in clinical laboratory testing may exclude a participant from trial participation. Any clinically significant change should be reported as an AE.

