## **14.4 Electrocardiogram**

Descriptive statistics will be presented for data related to ECGs (heart rate, RR interval, PR interval, QRS duration, QT interval, and QTcF interval). Change from baseline values will be presented for each post-baseline assessment.

Shift tables from baseline to each post-baseline visit and to each timepoint describing shifts to abnormality will be provided for overall interpretation. Only participants with a baseline result and a result at the specified visit for the parameter will be considered.

A listing of ECG assessments will be provided. In addition, a listing will be provided for each parameter where a participant had at least 1 abnormal result.

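### The SAP replaces any value with its retest in summaries; because on-treatment vital-sign repeats follow only out-of-range readings, the by-visit shift tables selectively lose abnormal readings.

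*SAP*

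**What the plan says.** SAP 5.6 sets one rule for repeats: "When retests measurements are done, the retest measurement will be used for the summary analysis". It does not distinguish a technically invalid first reading from a valid but abnormal one, and it applies to every parameter, arm and visit.

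The protocol says when repeats happen:

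- **Vital signs on treatment (Protocol 8.1.1):** "Values that are outside of the normal reference ranges at subsequent time points during the trial may be repeated", at the investigator's discretion.
- **Blood pressure at Screening or Day 1 (Protocol 8.1.1):** a reading above 160 mmHg systolic or 95 mmHg diastolic "must be confirmed by 1 repeat assessment in order to determine eligibility".
- **ECG at Screening or Day 1 (Protocol 4.2, exclusion 17a):** "Abnormal ECG may be repeated once".
- **Laboratory (Protocol 8.1.5, below Table 7):** a participant with a disqualifying screening value "may repeat the test once within the original screening time window".

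SAP 14.2 to 14.4 plan by-visit change from baseline and shift tables for laboratory, vital-sign and ECG data. The ECG shift tables are those "describing shifts to abnormality will be provided for overall interpretation". SAP 5.2 takes as baseline the last non-missing value up to first dose. On unscheduled data the SAP gives two rules: 5.6 keeps such assessments out of by-visit outputs, while 5.7.1 maps them to visit windows.

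**The concern.** Each repeat provision starts from an abnormal or disqualifying value, and nothing prompts a repeat of a normal one. If the repeat always replaces the first reading, the replacement is selected on the outcome being tabulated. An abnormal reading that regresses towards the participant's usual level leaves the table. A normal reading that would have been abnormal on a second measurement stays as it is.

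The clearest case is on-treatment vital signs, where the protocol itself permits such repeats after Day 1. Changes in vital signs, ECG and laboratory tests are stated safety endpoints, and the shift tables are where the arms are compared on abnormality. With about 30 participants per arm the counts are small, so losing one or two matters to how they read.

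**Working it through.** The documents give no abnormality rate, retest rate or measurement reliability, so there is no figure of theirs to reproduce. All inputs below are assumptions, except the arm size of about 30 (Protocol synopsis, Table 1).

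**Model.** First reading X1 and retest X2 are standard normal with correlation r. There is one upper limit c, and p = P(X1 > c). A share q of abnormal first readings is repeated, and the retest replaces the first reading.

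- Tabulated abnormal rate = p(1 − q) + q·P(X1 > c and X2 > c).
- Change in the visit mean, in SD units = −q(1 − r)·φ(c), where φ is the normal density.

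**Step 1: abnormal rate at a post-baseline visit, p = 5%.**

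| r | P(both > c) | Rate, q = 100% | Relative fall | Rate, q = 50% | Relative fall |
|---|---|---|---|---|---|
| 0.5 | 1.22% | 1.2% | 76% | 3.1% | 38% |
| 0.7 | 1.96% | 2.0% | 61% | 3.5% | 30% |
| 0.9 | 3.19% | 3.2% | 36% | 4.1% | 18% |

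Example for r = 0.5, q = 50%: 0.05 × 0.5 + 0.5 × 0.0122 = 0.0311. Over p = 2.5-10%, r = 0.5-0.9 and q = 50-100%, the relative fall runs from 16% (p = 10%, r = 0.9, q = 50%: 10% to 8.44%) to 82% (p = 2.5%, r = 0.5, q = 100%: 2.5% to 0.46%). Keeping the first reading leaves the rate at p.

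**Step 2: visit means.** Over the same grid the mean moves by −0.003 to −0.088 SD. The effect lies in counts and shift cells, not in means.

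**Step 3: normal-to-abnormal shift cell** (simulation, 2,000,000 draws, p = 5%, q = 100%, no treatment effect, correlation r between any two readings).

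| Replacement applied to | r = 0.5 | r = 0.7 | r = 0.9 |
|---|---|---|---|
| Neither | 3.8% | 3.1% | 1.8% |
| Post-baseline only | 0.7% | 0.8% | 0.7% |
| Baseline and post-baseline | 1.0% | 1.2% | 1.1% |
| Baseline only | 4.5% | 3.9% | 2.5% |

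The last row shows the opposite direction: a repeated pre-dose value makes baseline look more normal and raises apparent shifts to abnormal.

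**Step 4: comparison between arms** (vehicle 5% on first reading, active mean 0.5 SD higher, q = 100%).

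| | First readings | Retest rule (r = 0.5 / 0.7 / 0.9) |
|---|---|---|
| Risk difference, points | 7.6 | 3.3 / 4.3 / 5.7 |
| Risk ratio | 2.5 | 3.7 / 3.2 / 2.8 |
| Expected count per 30, vehicle | 1.5 | 0.4 / 0.6 / 1.0 |
| Expected count per 30, active | 3.8 | 1.4 / 1.9 / 2.7 |

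The absolute difference shrinks and the ratio grows.

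**The case against.** A reader might infer that the laboratory, vital-sign and ECG tables are all biased towards normal. The documents do not support that breadth.

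- **Laboratory and ECG.** Laboratory repeats are described only at screening, and the scheduled Day 1 sample normally supersedes that value as baseline. ECG repeats are described only at Screening and Day 1. The ECG shift table is of overall interpretation, so a count of QTcF above 450 ms is not a cell the SAP tabulates. SAP 5.6 would govern any on-treatment retest in these domains, but none is prescribed.
- **Direction.** It is not uniform, as the baseline-only row in Step 3 shows.
- **Masking.** It is tempting to say that the rule hides most in the arm with most excursions. That holds for absolute counts only. In Step 4 vehicle loses 76 / 61 / 36% of its abnormal readings and active 64 / 50 / 29%.
- **QTcF averaging.** The protocol provides that "the mean of the 2 QTcF assessments will determine eligibility". This is an eligibility rule, so it contrasts with SAP 5.6 without contradicting it. For blood pressure, the protocol's eligibility rule makes the repeat decisive, much as the SAP does.
- **Extent.** On-treatment repeats are discretionary, so 100% retesting is an upper case. At 50% the loss is half as large.

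The safeguards are real. All values are listed, with separate listings for participants who have an abnormal result. Findings judged clinically significant are reported as adverse events. SAP 5.6 also puts all safety data into non-by-visit summaries. But listings do not compare arms, and adverse events capture only what the investigator judges significant. SAP 14.2 to 14.4 name no worst-value or any-abnormality table by arm. These limits narrow the point; they do not justify an unconditional replacement rule.

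**Conclusion.** The point holds for post-baseline vital signs: followed as written, the plan selectively removes abnormal readings from the by-visit shift tables. It extends to laboratory and ECG data only if on-treatment retests occur there.

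The size is an illustration, not an estimate. It rests on a bivariate-normal test-retest model, a single limit, and assumed values of p, r and q. How far later-day retests enter the tables also depends on how the conflict between SAP 5.6 and 5.7.1 is settled. The documents do not support a general bias towards normal, a material effect on mean change from baseline, or a contradiction with the protocol's QTcF rule. No efficacy analysis is touched. It is a cheap improvement worth making before database lock.

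**What to change.** In SAP 5.6:

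1. Use the valid scheduled result in by-visit summaries and shift tables. Let a retest take its place only when that result is documented as invalid or is missing.
2. Add a by-arm summary of the worst post-baseline value for vital signs, laboratory and ECG, including retests and unscheduled results.
3. State, with SAP 5.2, which value is baseline when a pre-dose measurement is repeated, including QTcF and blood pressure. Otherwise the new table could pair a normalised baseline with a worst post-baseline value.
4. Reconcile SAP 5.6 with SAP 5.7.1, so that it is clear whether a retest at an unscheduled visit can enter a by-visit table.

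The cost is a few sentences and one extra table, with no new data. Reported abnormality rates will be slightly higher.
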